17.10 DEVICE-RELATED COMPLICATIONS

- Device embolization
 - Major: Device embolization that requires repeated catheterization or surgery or results in damage to surrounding cardiovascular structures.
 - Minor: Device embolization resolved by percutaneous retrieval during the procedure without surgical intervention or damage to surrounding cardiovascular structures.
- Device erosion
- Clinically significant device interference with surrounding structure (circumflex coronary artery, mitral valve, pulmonary artery, pulmonary vein)
- Device thrombus
- Device fracture
- Device infection/endocarditis/pericarditis
- Device perforation/laceration
- Device allergy.

17.11 DEVICE RELATED THROMBOSIS

DRT is a clot that forms on the atrial surface of the device during or after its implantation. However, there is currently no uniform definition or classification of DRT for LAA closure devices. The shape could be pedunculated or laminar. It can develop on many different parts of the device's surface, mostly on the central part of the lobe/disc (at the level of the pin) or in the recess adjacent to the Coumadin ridge.

This endpoint will be separately adjudicated by means of two imaging methods: TEE and CCTA.

TEE – DRT is defined at TEE evaluation as a homogenous mass with an echogenicity comparable to the myocardium on the atrial surface of the device, inconsistent with normal healing/device incorporation process and not explained by imaging artefact. DRT can have a pedunculated shape with an independent motion or be sessile without any motion and is visible in multiple planes. The occurrence of DRT will be locally ascertained at the very time of the TEE by an expert echocardiographer with extensive previous and ongoing work imaging on LAAC devices.

CCTA – DRT is defined at CCTA evaluation as homogenous hypoattenuated thickening (HAT) on the atrial surface of the device. Currently there is no uniform definition of DRT and differentiating it from prominent endothelialization by CCTA is not always easy. The occurrence of DRT will be centrally evaluated and adjudicated by the ICL, composed of three imaging experts who will independently score each of the studies as positive, possible or negative for DRT. In the event of inconsistent adjudication between the three readers, a consensus between all of them will be required. As previously suggested, assessment and scoring of HAT will be based on the following parameters: shape, maximum thickening, continuation onto the LA wall, HU HAT/HU LA ratio, cross sectional area at the base.

17.12 SUCCESS DEFINITIONS

Device success

- Device deployed and implanted in correct position

Technical success	
 Exclusion of the LAA No device-related complications No leak ≥ 3 mm on colour Doppler TEE
Procedural success	
 Technical success No procedure-related complications, except for uncomplicated (minor) device embolization.

17.13 LAA PATENCY ASSESSED BY TEE

At 45 days after LAAC, patients will undergo a TEE assessment (and a CCTA as well). Device deployment will be assessed from 0° to 135° (0° - 45° - 90° - 135°) with and without color Doppler (using a scale 50-60 cm/sec). Presence of leak will be locally ascertained by expert echocardiographers with extensive previous and ongoing work imaging on LAAC devices. Leak on TEE is defined as any jet between LAA and LA or conversely detectable by means of color-Doppler (high velocity 50-60 cm/sec). The size is measured taking the narrowest flow region of the jet that occurs at, or just close to, the device.

Of note, rate of LAA patency at 45 day CCTA will be compared with rate of leak at 45 day TEE.

17.14 FEASIBILITY OUTCOMES

During the index procedure, data related to number of device implantation attempts, total time procedure, x-ray dose and total contrast dose used in the procedure will be recorded (secondary endpoints).

Number of device implantation attempts

Device implantation attempt is defined as any delivery sheath retracting (or any advancement of device outside of delivery sheath in the event of “advancement technique” with Watchman FLX) aimed at exposing and implanting the device lobe. The number of partial and complete device recaptures will be recorder. Partial recapture is defined as the partial re-entry of the device into the delivery sheath keeping the hooks/anchors outside. Complete recapture is defined as the complete re-entry of the device into the delivery sheath (including the hooks/anchors).

Total time procedure

It refers to the time between the venous access puncture and its closure. In the event of a concomitant procedure performed right after LAAC, the ending time will be considered the time of device release.

X-ray dose procedure and total contrast dose procedure

Data related to X-ray and medium contrast doses used during LAAC will be recorded. In the event of a concomitant procedure, a careful differentiation between LAAC data and concomitant procedure data will be performed.

17.15 STAGING SYSTEM FOR ACUTE RENAL INJURY

Acute kidney injury (AKI) refers to an abrupt decrease in kidney function, resulting in the retention of urea and other nitrogenous waste products and in the dysregulation of extracellular volume and electrolytes. AKI will be adjudicated, according the latest Guidelines for AKI management,⁸ if one of the following criteria is met:

- Increase in serum creatinine by ≥ 0.3 mg/dL (≥ 26.5 micromol/L) within 48 hours;
- Increase in serum creatinine to ≥ 1.5 times baseline, which is known or presumed to have

occurred within the prior seven days;

- Urine volume <0.5 mL/kg/hour for six hours.

AKI will be subsequently staged for severity according to the criteria mentioned below.

Stage	Serum creatinine criteria	Urine output criteria
1	Increase in serum creatinine to 150–200% (1.5–1.99× increase compared with baseline) OR increase of ≥0.3 mg/dL (≥26.4 mmol/L)	Less than 0.5 mL/kg/h for more than 6 but <12 h
2	Increase in serum creatinine to 200–300% (2.0–2.99× increase compared with baseline)	Less than 0.5 mL/kg/h for more than 12 but <24 h
3	Increase in renal creatinine to ≥300% (.3× increase compared with baseline) OR serum creatinine of ≥4.0 mg/dL (≥354 mmol/L) with an acute increase of at least 0.5 mg/dL (44 mmol/L)	Less than 0.3 mL/kg/h for 24 h OR anuria for 12 h

1.1 Background and rationale

Non-valvular Atrial fibrillation (NVAF) is the most common cardiac arrhythmia and a major cause of morbidity and mortality because of cardioembolic stroke. Cardiac embolism due to AF causes up to 25% of all ischemic strokes, which makes it socioeconomically highly relevant. Oral anticoagulation (OAC) with vitamin K antagonists (VKA) or Non-vitamin K antagonist anticoagulant (NOAC) is the most effective prophylaxis for stroke in AF. Yet, (N)OAC therapy is associated with a significant bleeding liability and long-term (N)OAC therapy in patients with NVAF and concomitant high bleeding risk poses safety issues in a sizable and growing population in clinical practice. Post-mortem and echocardiographic studies have shown that the vast majority of all cardiac thrombi in patients with NVAF form in the left atrial appendage (LAA). Thus, a new and emerging therapeutic option in this high-risk patient population is the exclusion of the LAA cavity from the circulation via percutaneous intervention.

Currently, the Amplatzer ACP/Amulet™ (St. Jude Medical-Abbott), and the Watchman™ (Boston Scientific, Natick, MA, USA) are the devices with most clinical experience reported to date for percutaneous closure of LAA. The Watchman was tested in the setting of two randomized control trials, which demonstrated the safety of the procedure and the non-inferiority in terms of stroke reduction compared to OAC. A second-generation device, the Watchman FLX was developed and released for simplified implantation to fit a wider range of patients and to enhance sealing within the left atrial appendage. It gained the CE mark in the beginning of 2019.

Until a few years ago in Europe the device most frequently utilized for LAA closure was the Amplatzer Cardiac Plug™ (ACP, St. Jude Medical-Abbott), which gained CE approval in late 2008. There is no RCT comparing ACP with OAC, but many prospective and retrospective studies had shown the same safety profile and the non-inferiority with the OAC. A second-generation device, the Amulet™, was developed and released in 2013 for easier delivery, better coverage, and reduction of complications.

A critical step for each LAA closure procedure is the appraisal of LAA residual or new patency/leaks after device implantation. In the setting of available randomized trials (currently only limited to the Watchman device), successful closure was defined by the presence of a peridevice flow ≤ 5 mm assessed with TEE 45 days after the procedure. In these trials, as well as according to the current instruction for use of Watchman, the appraisal of residual leaks 45 days after LAAC was/is considered mandatory for a correct post procedural management of pharmacotherapy (in terms of continuation or reinstitution of OAC therapy). Furthermore, there is a growing attention to the natural history of peridevice leaks given their unpredictable evolution.

Currently the gold standard for the assessment of LAA patency after closure is the TEE. However it is an invasive and operator dependent examination, and replacing it with an alternative non-invasive exam is also desirable for patient's comfort

In the last years, several groups (including ours) assessed the value of CCTA as non-invasive post-procedural surveillance imaging modality after endovascular LAA closure to evaluate residual leak and reported higher sensitivity for CCTA as compared to TEE in the identification of LAA residual patency.

There are currently no randomized controlled trials assessing the degree of LAA closure between Amulet and Watchman/FLX.

1.2 Objectives

CTU Bern	Swiss APERO SAP	Version: 2.0	
	Template: CS_STA_TEM-11	Valid from: 17.08.2021	

The purpose of this study is to compare the efficacy and safety of the two devices for the LAAC, to assess whether Amplatzer Amulet is superior to Watchman/FLX in terms of degree of LAA occlusion as evaluated by CCTA 45 days after implantation.

The primary outcome is the composite of LAA patency at 45 day CCTA and the adjudicated crossover from one device to the other device based on morphological/anatomical considerations during device implantation, including failed implantation adjudicated cross-overs. Post-intervention LAA patency will also assessed via TEE based on the more conservative criterion of residual flow $\geq 3\text{mm}$.

CTU Bern	Swiss APERO SAP	Version: 2.0	
	Template: CS_STA_TEM-11	Valid from: 17.08.2021	

2. Study methods

2.1 Trial design

This will be a multicentre, open-label, prospective, randomized study in patients with AF and an indication for anticoagulant therapy with high bleeding risk, that agree to the LAAC procedure. Patients will be submitted to a screening protocol in a period not greater than 90 days before procedure, including medical and drug history, physical examination, 12-lead ECG, CCTA(as per standard of care) and TEE if clinically indicated.

Once the patient is judged eligible and the informed consent has been signed, the patient will be randomly assigned in a 1:1 to receive a LAAC with Amplatzer Amulet or Watchman/FLX device. In the event that the patient is randomized to the Watchman/FLX arm, the operator will be able to choose, on the basis of clinical reasons, if to implant Watchman or the new generation Watchman FLX (if available in the center).

Implantation will be performed according to common practice guidelines (and so with TEE/ICE guidance of procedure). Angiography at the end of the procedure is recommended to assess PDL. In case of concomitant procedure during LAAC, it will be reported separately in term of duration time, contrast dose and x-ray dose.

At the end of procedure, a measure of PDL must be provided.

A transthoracic echocardiogram is encouraged (but not mandatory) before the hospital discharge in order to detect pericardial effusion.

All patients randomly allocated to the Watchman/FLX or Amulet arm will receive ASA and clopidogrel or (N)OAC (at discretion of the treating physician and according to the bleeding risk, stroke risk as well as based on post-procedural TEE evaluation) for 45 days and then will undergo TEE assessment(as well as CCTA):

- *If a residual peri-device leak flow at 45 days > 5 mm or a intra-cardiac thrombus is detected, a therapy with ASA and (N)OAC could be considered up a sequential TEE evaluation at 6 months.*
- *If a residual peri-device leak flow at 45 days ≤ 5 mm is detected, patients will continue to receive ASA and clopidogrel or (N)OAC (at discretion of the treating physician according to the bleeding and stroke risk) up until 3 months after procedure. Thereafter, monotherapy with ASA will be continued until 12 months after procedure.*

These drug regimens are strongly recommended according the actually evidence and the instruction for use of the two devices. Nevertheless, if a clinical condition lead to prescribe other drugs regimen, it will be permitted given an exhaustive explanation by physician.

Further procedures, such as physical examination or blood sampling will be done according the study schedule, in particular visits or phone calls will take place after 6 and 13 month as well as 2/ 3/ 4/ 5 years.

2.2 Randomization

Balanced (1:1) randomization will be performed via a web-based interactive randomization system (ICE-Advice Pharma), based on a computer-generated random sequence with a random block size stratified according to site and an allocation to either Amulet Amplatzer device or Watchman/FLX. In the event that the patient is randomized to the Watchman/FLX arm, the operator will be able to choose, on the basis of clinical reasons, if to implant Watchman or the new generation Watchman FLX (if available in the center). Randomization will occur as close as possible to but always before the procedure and once the patient is judged eligible and the informed consent has been signed.

CTU Bern	Swiss APERO SAP	Version: 2.0	
	Template: CS_STA_TEM-11	Valid from: 17.08.2021	

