4.1 Confidence intervals and *P* values

Primary and secondary end points will be analysed on an intention-to-treat basis. Additional analyses will be also carried out in the per-protocol and as-treated populations. Categorical outcome measures will be compared using a χ^2 test or Fisher exact test as required. Continuous variables will be compared using a 2-sided unpaired t test or a Mann-Whitney test, as appropriate. Estimation of the cumulative incidence of safety and efficacy end-points will be performed using the Kaplan-Meier method in case of time-to-event endpoints, and event rates will be compared by the log rank test. The estimated relative risk (RR) is the ratio of the risk probabilities, and a confidence interval will be constructed based on a logarithmic transformation.

The primary endpoint LAA patency or adjudicated cross-over including failed cross-over to other device at 45 days will be analyzed using risk ratios and risk differences.

All statistical tests will be performed using a 5% significance level.

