two	count (%)	count (%)	x.xxx
Total nr of LAAC devices used			x.xxx
1	count (%)	count (%)	x.xxx
2	count (%)	count (%)	x.xxx
3	count (%)	count (%)	x.xxx
End of procedure cardiac rhyth no. (%)			x.xxx
Sinus	count (%)	count (%)	x.xxx
Atrial fibrillation or flutter	count (%)	count (%)	x.xxx
Pacemaker (incl temporary pacer)	count (%)	count (%)	x.xxx
Post-procedure peri-LAAC device leaks PDL — no. (%)			
Any PDL detected by TEE or Angiography?	count (%)	count (%)	x.xxx
detected by TEE only	count (%)	count (%)	x.xxx
detected by Angiography only	count (%)	count (%)	x.xxx
detected by TEE and Angiography	count (%)	count (%)	x.xxx
Periprocedural complications — no . (%)			
Death	count (%)	count (%)	x.xxx
Stroke or TIA	count (%)	count (%)	x.xxx
Bleeding	count (%)	count (%)	x.xxx
BARC 1	count (%)	count (%)	x.xxx
BARC 2	count (%)	count (%)	x.xxx
BARC 3abc	count (%)	count (%)	x.xxx
BARC 4	count (%)	count (%)	x.xxx
BARC 5ab	count (%)	count (%)	x.xxx
BARC 3-5	count (%)	count (%)	x.xxx
Peripheral or pulmonary embolization	count (%)	count (%)	x.xxx
Pericardial effusion (new onset)	count (%)	count (%)	x.xxx
Pericardial effusion clinically relevant	count (%)	count (%)	x.xxx

CTU Bern	Swiss APERO SAP	Version: 2.0	
	Template: CS_STA_TEM-11	Valid from: 17.08.2021	

Vascular access site complication	count (%)	count (%)	x.xxx
Device embolization	count (%)	count (%)	x.xxx
Acute kidney injury	count (%)	count (%)	x.xxx
Electrical or mechanical resuscitation	count (%)	count (%)	x.xxx

Data expressed as n (%), p-value from Fisher's tests) or means±standard deviations (p-value from unpaired t-tests) or median[IQR] (p-value from Mann-Whitney U-test).

LAAC: left-atrial appendage closure; PFO: patent foramen ovale; ASD: atrial septal defect; ICU: intensive care unit; TIA: transient ischemic attack; TEE: transoesophageal echocardiography.

* Coronary angiography included

CTU Bern	Swiss APERO SAP	Version: 2.0	
	Template: CS_STA_TEM-11	Valid from: 17.08.2021	

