OAC ***	count (%)	count (%)	x.xxx
SAPT+OAC	count (%)	count (%)	x.xxx
Triple therapy ***	count (%)	count (%)	x.xxx
Follow-up 45 days — no. (%) ¶	n=xx	n=xx	
Aspirin	count (%)	count (%)	x.xxx

CTU Bern	Swiss APERO SAP	Version: 2.0	
	Template: CS_STA_TEM-11	Valid from: 17.08.2021	

Clopidogrel	count (%)	count (%)	x.xxx
Prasugrel	count (%)	count (%)	x.xxx
Ticagrelor	count (%)	count (%)	x.xxx
Vitamin K-antagonist	count (%)	count (%)	x.xxx
NOAC	count (%)	count (%)	x.xxx
NOAC Type	count (%)	count (%)	x.xxx
Dabigatran	count (%)	count (%)	x.xxx
Rivaroxaban	count (%)	count (%)	x.xxx
Apixaban	count (%)	count (%)	x.xxx
Edoxaban	count (%)	count (%)	x.xxx
Others	count (%)	count (%)	x.xxx
Low-molecular weight heparin	count (%)	count (%)	x.xxx
Therapy	count (%)	count (%)	x.xxx
None	count (%)	count (%)	x.xxx
SAPT *	count (%)	count (%)	x.xxx
DAPT **	count (%)	count (%)	x.xxx
OAC ***	count (%)	count (%)	x.xxx
SAPT+OAC	count (%)	count (%)	x.xxx
Triple therapy ***	count (%)	count (%)	x.xxx

Data expressed as n (%) and p-values are from Fisher's tests.

* SAPT (Only Aspirin, Only Clopidogrel, Only Prasugrel, Only Ticagrelor)

** DAPT (Aspirin+Clopidogrel, Aspirin+Prasugrel, Aspirin+Ticagrelor)

*** OAC (NOAC, Vitamin K-Antagonist, Low molecular weight heparin)

**** Triple therapy (any combination between DAPT groups AND OAC groups)

§ within 6 hours of the device implantation

¥ xx patients died before discharge

¶ xx patients did not perform 45 day followup

CTU Bern	Swiss APERO SAP	Version: 2.0	
	Template: CS_STA_TEM-11	Valid from: 17.08.2021	

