5.7 Primary and secondary outcomes at 45 days of Follow-up

A Table of the primary and secondary outcomes at 45-day visit will be produced, randomized to Amulet vs randomized to Watchman

Table 4. Primary and secondary outcomes at 45 days

	Watchman/FLX	Amulet	Amulet vs Watchman Mean difference (95% CI)	p-value
	N = xx	N = xx		
Patent Appendage or justified cross-over to non-randomized device	n = xx, xx (%)	n = xx, xx (%)	x.x% (x.x%; x.x%)	x.XXX
Patent Appendage*	n = xx, xx (%)	n = xx, xx (%)	x.x% (x.x%; x.x%)	x.XXX
Justified cross-over to non-randomized device¶	n = xx, xx (%)	n = xx, xx (%)	x.x% (x.x%; x.x%)	x.XXX
Death	n = xx, xx (%)	n = xx, xx (%)	x.x% (x.x%; x.x%)	x.XXX
Cardiovascular death	n = xx, xx (%)	n = xx, xx (%)	x.x% (x.x%; x.x%)	x.XXX
Cerebrovascular event	n = xx, xx (%)	n = xx, xx (%)	x.x% (x.x%; x.x%)	x.XXX
Stroke	n = xx, xx (%)	n = xx, xx (%)	x.x% (x.x%; x.x%)	x.XXX
ischaemic stroke	n = xx, xx (%)	n = xx, xx (%)	x.x% (x.x%; x.x%)	x.XXX
haemorrhagic stroke	n = xx, xx (%)	n = xx, xx (%)	x.x% (x.x%; x.x%)	x.XXX
TIA	n = xx, xx (%)	n = xx, xx (%)	x.x% (x.x%; x.x%)	x.XXX
Systemic or pulmonary embolism	n = xx, xx (%)	n = xx, xx (%)	x.x% (x.x%; x.x%)	x.XXX
Systemic embolism	n = xx, xx (%)	n = xx, xx (%)	x.x% (x.x%; x.x%)	x.XXX
Pulmonary embolism	n = xx, xx (%)	n = xx, xx (%)	x.x% (x.x%; x.x%)	x.XXX
Myocardial infarction	n = xx, xx (%)	n = xx, xx (%)	x.x% (x.x%; x.x%)	x.XXX
Device embolization	n = xx, xx (%)	n = xx, xx (%)	x.x% (x.x%; x.x%)	x.XXX
Bleeding	n = xx, xx (%)	n = xx, xx (%)	x.x% (x.x%; x.x%)	x.XXX
BARC 2	n = xx, xx (%)	n = xx, xx (%)	x.x% (x.x%; x.x%)	x.XXX
BARC 3abc	n = xx, xx (%)	n = xx, xx (%)	x.x% (x.x%; x.x%)	x.XXX
BARC 4	n = xx, xx (%)	n = xx, xx (%)	x.x% (x.x%; x.x%)	x.XXX
BARC 5ab	n = xx, xx (%)	n = xx, xx (%)	x.x% (x.x%; x.x%)	x.XXX
BARC 3-5	n = xx, xx (%)	n = xx, xx (%)	x.x% (x.x%; x.x%)	x.XXX
TIMI major or minor	n = xx, xx (%)	n = xx, xx (%)	x.x% (x.x%; x.x%)	x.XXX
TIMI major	n = xx, xx (%)	n = xx, xx (%)	x.x% (x.x%; x.x%)	x.XXX
TIMI minor	n = xx, xx (%)	n = xx, xx (%)	x.x% (x.x%; x.x%)	x.XXX
TIMI minimal	n = xx, xx (%)	n = xx, xx (%)	x.x% (x.x%; x.x%)	x.XXX
GUSTO moderate or severe	n = xx, xx (%)	n = xx, xx (%)	x.x% (x.x%; x.x%)	x.XXX
GUSTO severe	n = xx, xx (%)	n = xx, xx (%)	x.x% (x.x%; x.x%)	x.XXX
GUSTO moderate	n = xx, xx (%)	n = xx, xx (%)	x.x% (x.x%; x.x%)	x.XXX
GUSTO mild	n = xx, xx (%)	n = xx, xx (%)	x.x% (x.x%; x.x%)	x.XXX
Patient on (N)OAC at 45 days visit	n = xx, xx (%)	n = xx, xx (%)	x.x% (x.x%; x.x%)	x.XXX

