Data expressed as n (%), p-value from Fisher's tests

¶ Justified crossover is defined as the switch from the randomized device to the other device based on morphological/anatomical considerations during device implantation as centrally assessed by an independent and multidisciplinary clinical event committee (CEC). This parameter was included in the composite primary outcome together with *LAA Patency.

CCTA: cardiac computer tomography angiography. TTE: Transthoracic Echocardiography.

CTU Bern	Swiss APERO SAP	Version: 2.0	
	Template: CS_STA_TEM-11	Valid from: 17.08.2021	

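### Site is the randomisation stratum but enters no planned analysis; the unstratified Fisher test on the primary outcome is valid but conservative, and a site-stratified test costs no patients

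*Combined protocol and SAP*

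**What the plan says.** - **Randomisation.** Protocol 6.2 and SAP 2.2 both describe a 1:1 allocation from a "computer-generated random sequence with a random block size stratified according to site". Site is the only stratification factor. SAP 2.2 also shows one way in which centres may differ: in the Watchman arm the operator may implant "the new generation Watchman FLX (if available in the center".
- **Primary test.** SAP 6.2.1 names no test, stratum or covariate. The first row of SAP Table 4 (section 5.7) is "Patent Appendage or justified cross-over to non-randomized device", and the footnote to that table reads "Data expressed as n (%), p-value from Fisher's tests". This is the only place where the SAP ties a test to the primary composite.
- **General rule.** SAP 4.1 and protocol 12.4 allow for categorical outcomes a chi-square "test or Fisher exact test as required". The footnotes to the other comparative tables agree with Table 4: "p-value from Fisher's tests" for Tables 2 and 5, "p-values are from Fisher's tests" for Table 3.
- **Effect measure.** SAP 4.1 says that the primary endpoint "will be analyzed using risk ratios and risk differences". It does not mention site.
- **Other analyses.** The long-term Cox models (SAP 6.2.2) compare the randomised arms only. The only covariate named anywhere is the CCTA delay (SAP 6.2.3). The subgroup list (SAP 6.2.4) omits site.
- **Power.** SAP 2.3 and protocol 12.2 state power above 80% with 200 patients, event rates of 50% and 30%, and alpha 5%.

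**The concern.** Blocking within site balances the arms inside each site. If sites differ in their event rates, this balance removes between-site variation from the treatment comparison. An unstratified test still counts that variation as noise, so its size falls below the nominal 5% and it loses power. Here a second source of conservatism is added: Fisher's exact test cannot attain 5% exactly because it is discrete. What is at stake is power for the primary claim. There is no risk of a false superiority claim from this source, because both effects act in the safe direction.

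**Working it through.** **Inputs from the documents:** 50% vs 30%, 200 patients, 1:1, alpha 5% (SAP 2.3, 2.2, 4.1). The sidedness of the primary test is not stated; two-sided is assumed. Protocol 14 mentions 4 main centres. The total number of sites, their sizes, the block sizes and the between-site variation are not given, so they are assumptions below.

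**Step 1. Reproduce the stated power.** Pooled normal formula with n = 100 per arm and mean rate 0.40:

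z = (0.20 × √100 − 1.96 × √(2 × 0.40 × 0.60)) / √(0.50 × 0.50 + 0.30 × 0.70) = (2 − 1.358) / 0.678 = 0.947, so power = 82.8%.

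The stated figure reproduces.

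**Step 2. Exact power and size, no site effect.** Full enumeration of both binomials at 100/100:

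| Test | Power, 50% vs 30% | Size, common rate 30-50% |
|---|---|---|
| Fisher | 79.2% | 3.5-4.0% |
| Chi-square, uncorrected | 83.2% | 5.1-5.6% |

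Fisher's exact power at other splits (Watchman/Amulet):

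| Split | 96/104 | 97/103 | 98/102 | 99/101 | 100/100 | 101/99 | 102/98 | 103/97 | 104/96 |
|---|---|---|---|---|---|---|---|---|---|
| Power | 81.2% | 81.6% | 80.9% | 80.1% | 79.2% | 82.4% | 81.6% | 80.9% | 81.1% |

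Only the exactly equal split falls below 80%.

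**Step 3. Add sites.** The CMH statistic without continuity correction is [Σ(aₛ − Eₛ)]² / ΣVₛ, summed over sites s. Here aₛ is the number of events in one arm, Eₛ = n₁ₛmₛ/Nₛ, and Vₛ = n₁ₛn₂ₛmₛ(Nₛ − mₛ) / [Nₛ²(Nₛ − 1)], with mₛ events among Nₛ patients. It is compared with 3.84.

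The simulation used 200,000 trials per setting, 200 analysed patients, permuted blocks of random size 2, 4 or 6 within site, normal site effects on the logit, and marginal rates held at 50% and 30%. The layouts were 4 equal sites, 4 sites at 50/25/15/10%, and 8 unequal sites without pooling. Arms came out exactly equal in only 29-41% of trials. Power in %:

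| Layout, site-logit SD | Fisher | Chi-square | CMH | CMH, corrected |
|---|---|---|---|---|
| 4 equal, 0 | 80.4 | 83.3 | 83.1 | 79.1 |
| 4 equal, 0.5 | 81.3 | 84.1 | 84.7 | 80.9 |
| 4 equal, 1.0 | 82.5 | 85.4 | 88.4 | 84.9 |
| 8 unequal, 0 | 80.5 | 83.2 | 82.6 | 78.6 |
| 8 unequal, 0.5 | 81.6 | 84.2 | 84.7 | 80.8 |
| 8 unequal, 1.0 | 82.7 | 85.3 | 88.5 | 85.0 |

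Size at common rates of 30-50%, for SD 0, 0.5 and 1.0: Fisher 3.9-4.5%, 3.5-4.0%, 2.8-3.1%; uncorrected CMH 4.9-5.4%, 4.9-5.1%, 4.9-5.0%.

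**Step 4. Separate the two causes.** Differences in power points over all layouts:

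| | SD 0 | SD 0.5 | SD 1.0 |
|---|---|---|---|
| CMH − Fisher (total) | 2.1 to 2.7 | 3.1 to 3.4 | 5.6 to 5.9 |
| CMH − chi-square (site alone) | −0.6 to −0.2 | +0.5 to +0.6 | +2.8 to +3.2 |

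For 4 equal sites at SD 0, for example: 83.1 − 80.4 = 2.7 and 83.1 − 83.3 = −0.2. With no site effect, the whole gain over Fisher comes from leaving Fisher.

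**Step 5. The one documented site difference.** Suppose FLX availability moves only the Watchman rate, by 5, 10 or 15 points up or down between centres (4 equal sites, 60,000 trials). CMH then differs from chi-square by −0.2 to +0.2 points. The larger gains need general site effects, which are assumed.

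**Step 6. Sensitivity to the balance assumption.** A separate simulation forced exact balance within site. CMH minus Fisher was then about 4 points at SD 0 and 7.5-8 at SD 1.0, mainly because exact balance puts Fisher at its weakest split. CMH minus chi-square was about 0 at SD 0, under 1 point up to SD 0.5, and about 4 points at SD 1.0.

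**The case against.** The strongest case against acting is that an unadjusted test after stratified randomisation is legitimate, and that most of the assured gain has nothing to do with site. Unstratified chi-square, which SAP 4.1 already permits, gains the same 2-3 points over Fisher. A site-logit SD of 1.0 means that sites one SD either side of a 50% site run at 27% and 73%. Nothing in the documents suggests so wide a spread, and several features work against it: fixed HU thresholds with core-lab consensus, a common CCTA protocol, and experienced or proctored operators. A pooling rule for small sites also adds a choice that Fisher does not need. All of this stands. It limits the size of the point but does not remove it, because the stratum is already in the design and using it is nearly free.

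Three stronger readings are tempting, and the documents do not support them:
- A reader might infer that the stated power is wrong, since Fisher gives 79.2% at 100/100. That holds only at the exactly equal split. Over the splits that site-stratified blocks produce, Fisher averages about 80.5%.
- A reader might infer that ignoring site costs the 2-3 points. Step 4 shows that it does not.
- A reader might infer that SAP 4.1 and Table 4 conflict. They do not: 4.1 permits Fisher, and Table 4 uses it.

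**Conclusion.** The point holds as a matter of efficiency and alignment. Site is the randomisation stratum and no planned analysis uses it. The planned Fisher test is valid but conservative, for two separate reasons: discreteness (size about 3.5-4.5% with no site effect) and the ignored stratum (about 3% at site-logit SD 1.0).

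Uncorrected CMH by site gains about 2-3 power points over Fisher if sites do not differ, and more if they do. The share due to site itself runs from about 0 to −0.6 points with no site effect, through about +0.5 at SD 0.5, to about +3 at SD 1.0. The last two figures rest on assumed site variation, and all of them on assumed site layouts and block sizes. Neither the validity of the primary result nor the stated power is in question. This is a change worth considering, not a correction of an error.

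**What to change.** 1. In SAP 6.2.1, name the CMH test stratified by randomisation site, two-sided 5%, as the primary test. Specify no continuity correction: with no site effect the corrected version has only about 79% power.
2. Report the Mantel-Haenszel site-stratified risk difference and risk ratio, each with a 95% CI. SAP 4.1 already plans both measures.
3. Stratify the Cox and log-rank analyses by site.
4. State any pooling rule for very small sites in the SAP before outcome data are examined by arm. This timing matters because, under SAP 2.8, the statistician who receives the raw data is not blinded.
5. Align SAP 4.1, the Table 4 footnote, protocol 12.4 and the synopsis. Keep Fisher for sparse secondary events.

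**Cost.** Wording, a pooling rule and a few lines of code; no extra patients. Fisher's strict size guarantee is lost (CMH size about 4.9-5.4%). If sites do not differ, up to about 0.6 points of power are given up against unstratified chi-square.
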